**Antiemetic prophylaxis with a 5-HT3-antagonist is strongly recommended.**

#### **4.4 General Concomitant Medication and Supportive Care Guidelines**

##### Prohibited Concomitant Medication During Study

Patients may receive other medications that the investigator deems to be medically necessary, with the specific exception of non-protocol specified chemotherapy, radiotherapy, anti-neoplastic biological therapy or other investigational agents. Patients who require the use of any of the aforementioned treatments for clinical management should be removed from the study.

##### Anticoagulants

Patients may not be on anticoagulation at study start but may be treated with anticoagulation therapy for medical reasons that occur on study.

##### Corticosteroids

Postoperatively, corticosteroids should be tapered to a stable dose as determined by the clinical status of the patient. The lowest required steroid dose should be maintained throughout the duration of the study in order to eliminate steroid effects as a confounding variable in the interpretation of serial brain imaging studies. Corticosteroid doses can be tapered as clinically indicated if the patient appears to be responding to therapy as judged by serial scans. Corticosteroid dose may, of course, be increased in the event of clinical deterioration or at the discretion of the attending physician. In the event of suspected clinical deterioration, repeat brain imaging is recommended.

##### Anticonvulsants

No data exist regarding the interaction of TRC102 with enzyme-inducing anti-epileptic drugs (EIAEDs). For this study, patients may **not** be on EIAEDs; patients who require anti-epileptic drugs (AED) may be on non-enzyme inducing anti-epileptic drugs (NEIAED). If a patient on this study protocol needs to have an AED started or needs to have a second AED added then only NEIAED should be used. There must be a  $\geq 10$  day period from discontinuation of an EIAED and initiation of therapy. In the event that an enzyme-inducing anti-epileptic drug must be used for a patient on study the patient will be removed from the protocol.

#### Herbal and Non-Traditional Medications

No data exist regarding the interaction of TRC102 with commonly used herbal or non-traditional medications. Patients should be instructed not to use such medications while receiving TRC102 therapy.

## **5.0 DOSING DELAYS/DOSE MODIFICATION FOR TOXICITY**

Clinically significant adverse events or abnormal laboratory values assessed as unrelated to disease progression, intercurrent illness, or concomitant medications require dose delay and dose modification. Such toxicities must have an attribution of possible, probable, or definite to TRC102 or temozolomide (see Section [9.2.2](#)).

In general, if toxicity occurs that is attributed to only one of the agents, only that agent should be dose-reduced/modified. The dose of the other agent can be maintained at the same level. If multiple toxicities occur, dose modification decisions should be based on the most severe toxicity.

**Because the protocol is designed to look at the effects of a combination treatment of TRC102 with TMZ, if either TRC102 or TMZ is permanently discontinued, the patient will be off treatment.**

For patients experiencing toxicity meeting the criteria below, the attributed drug(s) will be stopped. If the patient recovers ( $\leq$  grade 1 [or tolerable grade 2 for non-hematologic toxicity] or  $\leq$  baseline) a dose reduction is required for subsequent doses. Skipped doses will not be made up. If there is any question or confusion concerning a toxicity, the treating site should contact the ABTC Central Office to determine patient's toxicity status. The ABTC Central Office, with the Study Chair, will make the final decision.

- Hematological toxicities will require dose modification if any of the following occur and complete blood counts and differentials were obtained according to the mandated schedule (CBC, differential, and platelets drawn twice a week until the ANC  $\geq 1500/\text{mm}^3$  and platelets  $\geq 100,000/\text{mm}^3$ ): grade 3 or 4 lymphopenia will not be considered a toxicity requiring dose modification.

- ANC of  $< 500/\text{mm}^3$ .

- Platelets < 25,000/mm^3.
- Febrile neutropenia
- Any hematological toxicity that prevents administration of > 80% of the planned TRC102 and temozolomide doses

➤ Non-hematological toxicities will require dose modification if any of the following occur:

- Grades 3-4 severity (except nausea, vomiting, and diarrhea without sufficient prophylaxis; except alopecia; except grade 3 hyperglycemia; except grade 3 electrolyte disturbances that are asymptomatic and that respond to replacement therapy; and except grade 3 neurologic toxicity responding within two weeks to steroids, anticonvulsants, or electrolyte correction. A subject's first episode of deep venous thrombosis (DVT) or pulmonary embolism (PE) will not require dose modification.)

*ANY TOXICITY (AS DEFINED ABOVE) CAUSING DELAY IN TREATMENT OF OVER 21 DAYS IN THE START OF A CYCLE WOULD RESULT IN TAKING THE PATIENT OFF TREATMENT.*

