### 5.1 Dose Modification for TRC102

The dose levels and the general approach to TRC102 dose modification on this trial are shown below. Adverse events (AEs) should be treated with the appropriate maximum supportive care, and dose reductions should be clearly recorded on the case report form.

Dose reductions are required for any clinically significant toxicity as defined above. Dosing will stop until the toxicity has resolved to ≤ grade 1 (or tolerable grade 2 for non-hematologic toxicity) or ≤ baseline. The maximum length of time that TRC102 can be held is 21 days. If treatment-related toxicity is not resolved in ≤ 21 days, the patient will be removed from treatment. After resolution, when dose reduction is permitted, the dose of TRC102 will be modified as stipulated below, with a maximum of 2 dose reductions. If there is any question, the ABTC Central Office and the Study Chair should be contacted.

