#### Dose Reduction Table for TRC102

Dose Level	TRC102
Starting dose	150mg flat dose
First dose reduction	125mg flat dose
Second dose reduction	100mg flat dose

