### 5.2 Dose Modification for Temozolomide

Clinically significant toxicities having an attribution to TMZ of possible, probable or definite will result in the following TMZ dose modifications. Dosing is based on toxicity during the prior treatment cycle. If multiple toxicities are seen, the dose administered should be based on the dose reduction required for the most severe grade of any single toxicity.

Blood counts will be evaluated weekly. Within -5 days prior to first dose of each 5-day TMZ treatment the patient must have an ANC  $\geq 1500/\text{ul}$  and platelet count  $\geq 100,000/\text{ul}$ . On Day 1 of each cycle (within -5 days) all **non-hematological** toxicity grade 3 or 4 (except for alopecia, nausea and vomiting) must have resolved (CTCAE grade  $\leq 1$  [or tolerable grade 2]). If toxicity persists, treatment should be delayed by one week for up to 3 consecutive weeks. If after 3 weeks of delay all toxicity has still not resolved then any further treatment with temozolomide should be stopped (patient is off treatment).

**Dose reductions:** If any non-hematological toxicity observed during the most recent pre-cycle evaluation was CTCAE **Grade > 2** (except for alopecia, nausea and vomiting) **and/or if platelets < 50,000/ul and/or ANC < 1000/ul**, then the dose should be reduced by one dose level (see table below). For patients who would require dose reductions to a dose level  $< 100\text{mg}/\text{m}^2/\text{day}$ , temozolomide will be **stopped**. Also, if any of the same non-hematological **Grade 3 toxicity recurs** (except for alopecia, nausea and vomiting) after reduction for that toxicity, then temozolomide will be **stopped** (patient is off treatment).

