## 9.0 MONITORING OF PATIENTS

### 9.1 Table of Required Observations

#### Arms 1 & 2 (28-Day Cycles)

	Baseline	Days 1-5 of every cycle	Weekly During Cycle 1	Weekly During All Cycles	Pre-Odd Cycles (cycles 3+)	Pre- Even Cycles	Off Treatment	30 Days post-last dose
TRC102		6						
Temozolomide		7						
Glucocorticoids Dose Evaluation	1				5		8	
AE Evaluation	1		12		5	5	8,10	11
MRI	1				5		8	
H&P/Neuro Exam	1				5	5	8	
KPS	1				5	5	8	
Vital Signs	1,2		12		2,5	2,5	2,8	
CBC, Diff, Platelets	1			9,12	5,9	5,9	8,9	
Serum Chemistry	1,3		12		3,5	3,5	3,8	
APTT or PTT	1							
Serum Pregnancy Test	1,4							
Archived Tumor Tissue	13							

- 1– All baseline measurements must be done within minus 21 calendar days of treatment administration unless otherwise specified.
- 2– Including blood pressure, respiratory rate, heart rate, temperature, weight, height: height is required at baseline only; weight is required at pre-odd cycle evaluations only.
- 3– Including albumin, alkaline phosphatase, total bilirubin, calcium, creatinine, magnesium, phosphorus, potassium, SGOT, SGPT, sodium.
- 4– For women of child-bearing potential.
- 5– Within minus 5 calendar days of cycle start.
- 6– TRC102 is administered orally on Days 1-5 of each 28-day cycle (see Section [4.3.1](#)). Patients are required to keep a medication diary.
- 7– Temozolomide is administered orally on Days 1-5 of each 28-day cycle (see Section [4.3.2](#)). Patients are required to keep a medication diary.
- 8– Evaluations done within +7 days of off treatment date unless indicated: do not repeat: if MRI within minus 14 days of off-treatment date; if H&P/neuro, KPS, labs within minus 5 days of off-treatment date.
- 9– If ANC < 1500 or plts < 100,000, CBCs/differentials will be repeated twice a week until counts are recovered (ANC  $\geq$ 1500 or plts  $\geq$ 100,000) per protocol. If counts are recovered (ANC  $\geq$ 1500 or plts  $\geq$ 100,000) on day of scheduled drawing do not repeat until next protocol schedule day
- 10 – Adverse Events must be followed for at least 30 days from last dose of TRC102.
- 11– Perform within +14 days of the 30-day post-last dose date.
- 12–  $\pm$  1 day
- 13– Unstained slides from initial resection at diagnosis of glioblastoma, if available (see Section [9.5.1](#))

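### Section 5.0 makes its hematologic dose-modification triggers depend on blood counts having been drawn on schedule, so a missed draw can waive a required TRC102 reduction

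*Combined protocol and SAP*

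**What the plan says.** Section 5.0 opens with a general statement: clinically significant events or laboratory abnormalities not explained by progression, "intercurrent illness, or concomitant medications require dose delay and dose modification", provided they are at least possibly attributed to TRC102 or temozolomide. The working instruction follows. When a toxicity meets the criteria listed further down, the attributed drug is stopped, and after recovery it resumes at a reduced dose.

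The hematologic list applies "if any of the following occur and complete blood counts and differentials were obtained according to the mandated schedule". A parenthesis gives that schedule as twice-weekly draws until ANC is at least 1500 and platelets are at least 100,000. The same sentence exempts lymphopenia. Four triggers follow: ANC below 500, platelets below 25,000, febrile neutropenia, and "Any hematological toxicity that prevents administration of > 80% of the planned TRC102 and temozolomide doses".

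The other list in Section 5.0 has no monitoring condition: "Non-hematological toxicities will require dose modification if any of the following occur".

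For TRC102, Section 5.1 says "Dose reductions are required for any clinically significant toxicity as defined above" and adds no count limits. The first step down from 150 mg in its table is "125mg flat dose". For temozolomide, Section 5.2 requires one dose level down at platelets below 50,000 and/or ANC below 1000, again with no monitoring condition.

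Table 9.1, footnote 9, says that when ANC is below 1500 or platelets are below 100,000, "CBCs/differentials will be repeated twice a week until counts are recovered". It twice defines recovery as ANC at least 1500 *or* platelets at least 100,000, where Section 5.0 uses *and*.

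**The concern.** Whether a severe cytopenia leads to a lower TRC102 dose should depend on the cytopenia. As worded, it also depends on whether every required draw was made. The patient with incomplete monitoring, whose lowest count is known least well, has the weaker protection. The named twice-weekly schedule starts only once counts are already low, so that part of the condition can fail only in patients who already have a low count. What is at stake is the TRC102 dose given after recovery.

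**Working it through.** No calculated figure in the plan bears on this point. The check sets the rules side by side, with simple arithmetic for size.

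**1. Which rules carry the condition**

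| Rule | Triggers | CBCs on schedule needed? | Drug changed |
|---|---|---|---|
| 5.0, hematologic | ANC <500; platelets <25,000; febrile neutropenia; toxicity preventing dosing | Yes, for 4 of 4 | Attributed drug(s) |
| 5.0, non-hematologic | Grade 3-4, with exceptions | No | Attributed drug(s) |
| 5.1 | None of its own; refers back | As in 5.0 | TRC102 |
| 5.2 | ANC <1000; platelets <50,000; non-hematologic above grade 2 | No | Temozolomide |

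**2. One case followed through.** Take an ANC below 500 attributed to TRC102, with one required repeat draw missed.

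- The event part of the trigger is met; the schedule part is not. The toxicity therefore falls outside the list.
- The instruction to stop and then reduce covers only toxicity that meets the listed criteria, so it does not apply.
- Section 5.1 sends the reader back to Section 5.0 and supplies no threshold that would rescue the reduction.
- Literal result: no TRC102 reduction is required.

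**3. What Section 5.2 covers.** Comparing thresholds, 500/1000 = 0.5 for ANC and 25,000/50,000 = 0.5 for platelets. Any ANC or platelet event that meets Section 5.0 is therefore also below the Section 5.2 limit. If it is at least possibly attributed to temozolomide, that drug is reduced whatever the draw history. This gives 2 of the 4 triggers an explicit unconditional counterpart, but for temozolomide only. Section 5.0 says that when one agent alone is implicated, only that agent is changed. When both are implicated, Section 5.2 lowers temozolomide and leaves the TRC102 step to Section 5.0.

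**4. Size of the step left open.** TRC102 would go from 150 to 125 mg: (150 − 125)/150 = 16.7%. Over a five-day cycle, 5 × 150 = 750 mg against 5 × 125 = 625 mg, a difference of 125 mg.

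**5. The two recovery definitions.** Suppose ANC is 1,600 and platelets are 40,000. Under footnote 9 read literally, one count is above its limit, so the patient has recovered and twice-weekly draws stop. Under Section 5.0 they must continue. If the next weekly draw shows platelets of 20,000, the platelet trigger is met, but the Section 5.0 schedule was not followed. A site that obeyed footnote 9 would have failed the condition in Section 5.0.

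**The case against.** The best defence is that the gap is small and already guarded.

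- TRC102 is given only on days 1-5. Section 4.2 bars the next cycle until ANC is at least 1500, platelets are at least 100,000 and toxicities have recovered.
- Twice-weekly draws start after a low count has been seen, so a missed repeat does not mean the problem went unnoticed.
- Attribution need only be possible. Temozolomide is a known cause of cytopenia taken at the same time, so Section 5.2 will often act.
- Sections 5.0 and 5.1 send doubtful cases to the Central Office and Study Chair.

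All of this stands, and it keeps the point minor. It does not remove the point. The recovery requirements decide when dosing resumes, not at what TRC102 dose. Section 5.2 changes temozolomide only. Central review depends on a site seeing a question, and a site that reads the list literally may see none. The *or* in footnote 9 is probably a slip, but it is a real mismatch with Section 5.0.

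Two stronger readings are tempting, and the documents do not support them. A reader might infer that Section 5.0 contains two contradictory rules, because its opening sentence has no monitoring condition. That sentence sets no threshold, however, and the instruction after it limits action to toxicity on the list. It is better read as a general statement made specific, which leaves one badly worded condition. A reader might also infer a particular gap for anemia, which the TRC102 risk list gives as possibly related. Neither Section 5.0 nor Section 5.2 has a hemoglobin threshold, and deleting the condition would not create one. Anemia is mostly a separate matter.

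**Conclusion.** The point holds as a minor wording defect in a safety rule. All four listed hematologic triggers carry a condition that does not belong in a trigger. Read literally, it removes the required TRC102 step from 150 to 125 mg after a qualifying TRC102-attributed cytopenia when a draw was missed.

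This rests on three conditions: the sentence is applied as written, the event is attributed to TRC102, and the schedule was not fully kept. The 16.7% is simply the protocol's own reduction step; it does not measure harm. The documents give no rate of TRC102-attributed cytopenia and no rate of missed draws, so frequency cannot be estimated.

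A reader might go on to infer that patients could be re-dosed while their counts are low, or that the efficacy conclusions are affected. Neither follows. The Section 4.2 requirements do not depend on draw history. The response criteria, sample sizes and stopping boundaries in Section 11.0 make no use of this list.

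**What to change.** In Section 5.0, end the hematologic lead-in after *occur*, followed by a colon and the four triggers. Keep the lymphopenia exception as its own sentence. State the twice-weekly CBC schedule as a separate monitoring instruction, and add that a missed draw does not waive dose modification.

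Separately, in Table 9.1, footnote 9, change *or* to *and* in both recovery definitions, so that repeat draws continue until ANC is at least 1500 and platelets are at least 100,000, as Section 5.0 requires.

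The cost is one sentence split, one sentence added and two one-word changes. No draws are added beyond those Section 5.0 already mandates. The only downside is possibly a few more TRC102 reductions.

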### 5.1 Dose Modification for TRC102

The dose levels and the general approach to TRC102 dose modification on this trial are shown below. Adverse events (AEs) should be treated with the appropriate maximum supportive care, and dose reductions should be clearly recorded on the case report form.

Dose reductions are required for any clinically significant toxicity as defined above. Dosing will stop until the toxicity has resolved to ≤ grade 1 (or tolerable grade 2 for non-hematologic toxicity) or ≤ baseline. The maximum length of time that TRC102 can be held is 21 days. If treatment-related toxicity is not resolved in ≤ 21 days, the patient will be removed from treatment. After resolution, when dose reduction is permitted, the dose of TRC102 will be modified as stipulated below, with a maximum of 2 dose reductions. If there is any question, the ABTC Central Office and the Study Chair should be contacted.

#### Dose Reduction Table for TRC102

Dose Level	TRC102
Starting dose	150mg flat dose
First dose reduction	125mg flat dose
Second dose reduction	100mg flat dose

### 5.2 Dose Modification for Temozolomide

Clinically significant toxicities having an attribution to TMZ of possible, probable or definite will result in the following TMZ dose modifications. Dosing is based on toxicity during the prior treatment cycle. If multiple toxicities are seen, the dose administered should be based on the dose reduction required for the most severe grade of any single toxicity.

Blood counts will be evaluated weekly. Within -5 days prior to first dose of each 5-day TMZ treatment the patient must have an ANC  $\geq 1500/\text{ul}$  and platelet count  $\geq 100,000/\text{ul}$ . On Day 1 of each cycle (within -5 days) all **non-hematological** toxicity grade 3 or 4 (except for alopecia, nausea and vomiting) must have resolved (CTCAE grade  $\leq 1$  [or tolerable grade 2]). If toxicity persists, treatment should be delayed by one week for up to 3 consecutive weeks. If after 3 weeks of delay all toxicity has still not resolved then any further treatment with temozolomide should be stopped (patient is off treatment).

**Dose reductions:** If any non-hematological toxicity observed during the most recent pre-cycle evaluation was CTCAE **Grade > 2** (except for alopecia, nausea and vomiting) **and/or if platelets < 50,000/ul and/or ANC < 1000/ul**, then the dose should be reduced by one dose level (see table below). For patients who would require dose reductions to a dose level  $< 100\text{mg}/\text{m}^2/\text{day}$ , temozolomide will be **stopped**. Also, if any of the same non-hematological **Grade 3 toxicity recurs** (except for alopecia, nausea and vomiting) after reduction for that toxicity, then temozolomide will be **stopped** (patient is off treatment).

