### 9.2.1.2 Adverse Event List for Temozolomide

Known potential toxicities of temozolomide are hematological toxicities (leucopenia, lymphopenia, thrombocytopenia, and anemia), renal insufficiency, nausea and vomiting, liver enzyme abnormalities, lethargy, rash, headache, alopecia, constipation, fatigue/malaise, anorexia, hyperglycemia and diarrhea are known toxicities. Recently, cases of hepatic injury, including fatal hepatic failure, have been observed in patients enrolled in clinical studies utilizing the agent temozolomide. In addition, it was noted that liver toxicity may occur several weeks or more after initiation of treatment or after temozolomide discontinuation. Refer to the package insert for additional information on adverse events observed to date.

Rats given temozolomide in recent multidose toxicity studies have developed adenocarcinoma of the breast, fibrosarcomas, malignant Schwannomas (a variant of fibrosarcoma), keratoacanthomas and basal cell adenomas. Similar studies conducted in dogs did not reveal any similar findings. The significance of this finding for humans is not known presently.

Temozolomide is potentially mutagenic and should be handled with appropriate precautions by both staff and subjects. Subjects with known or suspected hypersensitivity to temozolomide should not be treated with temozolomide. There are no data available on the effect or management of temozolomide overdose.

Additional information is available in the temozolomide package insert ([www.temodar.com](http://www.temodar.com)).

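### For non-hematologic toxicity at least possibly due to temozolomide, sections 5.0 and 5.2 list different exempt events, and nothing says which list governs the temozolomide dose

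*Combined protocol and SAP*

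**What the plan says.** Section 5.0 is not confined to TRC102. It states: "Such toxicities must have an attribution of possible, probable, or definite to TRC102 or temozolomide". When its criteria are met, the attributed drug is stopped, and after recovery "a dose reduction is required for subsequent doses". Among non-hematologic events, grades 3 and 4 meet the criteria apart from a list of exceptions:

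- for gastrointestinal events, alopecia and glucose: "except nausea, vomiting, and diarrhea without sufficient prophylaxis; except alopecia; except grade 3 hyperglycemia"
- for electrolytes, a grade 3 disturbance without symptoms that replacement corrects
- for the nervous system, a grade 3 event that settles inside two weeks on treatment
- for thromboembolism: "A subject's first episode of deep venous thrombosis (DVT) or pulmonary embolism (PE) will not require dose modification" (no grade limit is given)

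Section 5.2 sets rules for temozolomide alone, for toxicity at least possibly attributed to it. Non-hematologic toxicity above grade 2 costs one dose level. Recurrence of the same grade 3 toxicity after a reduction stops the drug, and so does any grade 4 event. Each of these three rules carries the same short list of exceptions: alopecia, nausea and vomiting. The recurrence rule is worded "except for alopecia, nausea and vomiting) after reduction for that toxicity, then temozolomide will be" stopped.

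Section 4.3.2 sends non-hematologic toxicity of grade 3 or higher in the first cycle to section 5.2, and that sentence names no exception. Sections 4.1 and 5.0 both say that permanent discontinuation of either drug takes the patient off treatment.

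**The concern.** Two rules apply to the same drug and the same event and give different instructions. A site that reads 5.0 leaves the temozolomide dose alone; a site that reads 5.2 reduces or stops it. Some of the events are foreseeable from the protocol itself: the temozolomide adverse event list in 9.2.1.2 says "constipation, fatigue/malaise, anorexia, hyperglycemia and diarrhea are known toxicities", and an attribution of possible is enough to bring an event under either section. What is at stake is uniform handling of toxicity across a multicenter trial: who is reduced, and who leaves the combination.

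**Working it through.** The plan gives no figure to reproduce. The check compares the two sections for an event that is at least possibly attributed to temozolomide and not to progression, intercurrent illness or concomitant medication.

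| Event | Section 5.0 | Section 5.2 |
|---|---|---|
| Grade 3 hyperglycemia | No modification | One level down |
| Grade 3 electrolyte disturbance, asymptomatic and correctable | No modification | One level down |
| Grade 3 neurologic toxicity, responds within two weeks | No modification | One level down |
| Grade 3 diarrhea without sufficient prophylaxis | No modification | One level down |
| Grade 4 diarrhea without sufficient prophylaxis | No modification | Stop |
| First DVT or PE, grade 3 | No modification | One level down |
| First DVT or PE, grade 4 | No modification | Stop |
| Grade 3-4 nausea or vomiting despite sufficient prophylaxis | Hold, then reduce | Exempt |
| Nausea or vomiting without sufficient prophylaxis | Exempt | Exempt |
| Alopecia | Exempt | Exempt |
| Grade 3 diarrhea despite sufficient prophylaxis | Hold, then reduce | One level down |

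Five event types are exempt in 5.0 only, one conflicts in the reverse direction, and the last three rows agree.

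**Size of one step.** The temozolomide table goes from 150 to 100 mg/m², then off treatment. The single step is (150 − 100) / 150 = 50 / 150 = 33%.

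**Two events in sequence, 5.2 applied literally.** The first grade 3 event takes the dose to 100 mg/m². If the same toxicity returns at grade 3, the recurrence rule stops temozolomide. If a different grade 3 toxicity calls for another reduction, the dose would fall below 100 mg/m², which 5.2 also treats as a stop. Either way both drugs end.

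**The same sequence under 5.0.** Two episodes of grade 3 hyperglycemia, of correctable grade 3 electrolyte disturbance or of transient grade 3 neurologic toxicity leave the dose at 150 mg/m². For DVT or PE, only the first episode is protected.

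**Is precedence stated?** Section 5.1 (TRC102) refers back to the definition of toxicity given in 5.0. Section 5.2 has no such reference. It also sets its own hematologic triggers (ANC below 1000 and platelets below 50,000, against below 500 and below 25,000 in 5.0), so it reads as self-contained. Yet 5.0 names temozolomide, and no sentence says that 5.2 overrides it.

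**Which observation counts?** The reduction sentence in 5.2 looks at the evaluation just before the cycle. The opening paragraph of 5.2, and the paragraph on subsequent treatments, look at the whole preceding cycle. A neurologic or electrolyte event that has settled by the pre-cycle visit triggers a reduction under the second wording but perhaps not under the first.

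**The case against.** The best defence is that the sections can be harmonized. The opening of 5.2 speaks of clinically significant toxicities, as 5.0 and 5.1 do, so the 5.0 exceptions might be carried over. Alternatively, 5.2 might prevail as the drug-specific rule. Either is a fair reading, but neither is written, and they give opposite doses for the same patient. That is the difficulty, not an answer to it.

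A second defence is central adjudication. Section 5.0 refers doubtful cases to the ABTC Central Office, which decides with the study chair. This softens the problem, but it works only when a site sees that there is a question. A site following one section alone may see none.

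Other limits stand in full. Section 5.0 removes events judged due to progression, intercurrent illness or concomitant medication. An event attributed only to TRC102 falls under 5.0 and 5.1, which agree. Thromboembolic events appear in the TRC102 list with relationship undetermined and not in the temozolomide list in 9.2.1.2, so the DVT/PE conflict needs an investigator to judge temozolomide a possible cause.

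A reader might go further in four ways that the documents do not support:

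- The cycle-start conditions might seem to contradict the 5.0 exemptions. They do not: 5.0 waives modification, not recovery, and section 4.2 separately requires recovery before every cycle with no list of exceptions.
- The corticosteroid paragraph in 4.4 might be taken to make the hyperglycemia conflict common. Hyperglycemia judged due to steroids is filtered out by 5.0.
- The anticoagulant paragraph in 4.4 might be taken to anticipate DVT or PE. It mentions neither.
- An effect on the response endpoint might be inferred. Nothing in the documents allows its size or direction to be assessed.

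**Conclusion.** The point stands as an internal inconsistency that should be corrected, limited to non-hematologic events at least possibly attributed to temozolomide. For a given patient the gap lies between no change and a 33% cut at the first grade 3 event, and between staying on and leaving both drugs at a recurrence. For a first DVT or PE, or under-prophylaxed diarrhea, at grade 4, it lies between no change and off treatment at once.

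Three conditions apply:

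- The 5.0 exemptions for diarrhea and for neurologic toxicity are conditional, so not every such event conflicts.
- The nausea and vomiting mismatch assumes that the phrase about prophylaxis in 5.0 covers all three gastrointestinal terms. If it covers diarrhea alone, that row drops out and the other five remain.
- It would be too strong to say that every such grade 3 event costs a dose level, because the two windows in 5.2 leave resolved events open.

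No frequency for any of these events is given, so the number of patients affected is unknown. This review takes no position on which rule is clinically right.

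**What to change.** Reconcile sections 4.3.2, 5.0 and 5.2 in one of two ways:

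- State a single list of exempt non-hematologic events, and have the first-cycle sentence in 4.3.2 and the reduction, recurrence and grade 4 sentences in 5.2 refer to it. The grade 4 sentence must be included, or the ungraded DVT/PE exemption will still conflict with it.
- If temozolomide is meant to have its own list, state which section prevails for temozolomide.

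In either case, say whether 5.2 acts on the pre-cycle evaluation or on the worst grade in the preceding cycle, and make clear which gastrointestinal terms the prophylaxis condition covers. The study chair decides the content of the list and the window.

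The cost is a wording amendment. It needs no new data and no change to the sample size.
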